#### Urine renal safety biomarkers

- Albumin
- Total protein
- Creatinine
- Urine protein to creatinine ratio (UPCR)
- Urine albumin to creatinine ratio (UACR)
- Estimated glomerular filtration rate (eGFR; by CKD-EPI formula)

#### Other Laboratory Assessments

- Complement activation panel (C3a, Bb, C5a)

- hs-CRP

Safety clinical laboratory parameters are assigned to the analysis visits and the study phases as described in section 3.1.2 and section 3.1.3 respectively. Evaluations with missing or partially missing dates cannot be imputed to any study phase and analysis visit.

Safety clinical laboratory results below the LLOQ for which the exact value cannot be determined, will be replaced with the LLOQ divided by the squared root of 2.

After the LLOQ replacement, change from baseline to each post-baseline visit for safety clinical laboratory results is defined as the post-baseline visit value minus the baseline visit value; percent change from baseline to each post-baseline visit for platelet count is defined as the post-baseline visit value minus the baseline visit value divided by the baseline visit value \*100.

After the LLOQ replacement, Safety clinical laboratory results except urine renal safety biomarkers and other laboratory assessments are also classified as normal (if value is within normal reference range), low (if value is below the normal reference range), and high (if value is above the normal reference range) based on the reference range indicator.

After the LLOQ replacement, AST, ALT and TBL are also classified as below:

AST and ALT:

- $<3xULN$  (or below the LLOQ)
- $\geq 3 - <5xULN$
- $\geq 5 - <8xULN$
- $\geq 8xULN$

TBL:

- $<1 xULN$  (or below the LLOQ)
- $\geq 1 - <2xULN$
- $\geq 2xULN$

Occurrences of AST or ALT  $\geq 3 \times ULN$  together with TBL  $\geq 2 \times ULN$  are reported as SAE (Potential Hy's law) as described in the study protocol.

### 3.3.3.3 Vital signs

Vital signs include:

- Systolic blood pressure (mmHg)
- Diastolic blood pressure (mmHg)
- Pulse rate (bpm)
- Temperature (C)

Vital signs parameters are assigned to the analysis visits and analysis phases as described in sections 3.1.2 and 3.1.3. Evaluations with missing or partially missing dates cannot be imputed to any analysis visit / analysis phase.

Change from baseline is defined as the post-baseline visit value minus the baseline value.

Additionally, vital signs values will be classified as normal (if value is within normal reference range), low (if value is below the normal reference range), and high (if value is above the normal reference range) according to the normal reference ranges:

**Table 6 Vital signs normal reference ranges**

Parameter	Normal Reference Ranges
Systolic blood pressure	80 - 160 mmHg
Diastolic blood pressure	50 -90 mmHg
Heart rate	50 - 100 bpm
Temperature	<=37°C

### 3.3.3.4 Weight and BMI

BMI (kg/m^2) is calculated as: weight (kg) / [(height (cm)/100)]. Weight (kg) and BMI (kg/m^2) are assigned to analysis visits as described in section 3.1.2. Evaluations with missing or partially missing dates cannot be imputed to any study phase and analysis visit. Change from baseline is defined as the post-baseline visit value minus the baseline value.

### 3.3.3.5 ECG

ECG parameters includes the following:

- RR (msec)
- PR (msec)
- QRS (msec)
- QT (msec)
- QTcF (msec)
- HR (beats/min)
- Overall evaluation (normal, abnormal). If abnormal also reason and clinically significance is collected

For each participant, RR, PR, QRS and QT will be calculated as follow: the mean value of all measurements will be taken provided that at least 2 measurements are present (and at least 3 consecutive beats were analysable in each ECG) or else, the averaged value at the corresponding target time point will be set to missing. QTcF will be calculated as  $QTcF = QT * RR^{-1/3}$ , where the QT interval is in milliseconds and the RR interval is in seconds. Heart rate will be calculated, based on the RR interval as  $HR = 60 / RR$  interval, where the RR interval is in seconds. Calculation of derived parameters will be performed after averaging of QT and RR data. Results from these calculations will be reported in the eCRF together with the overall evaluation.

ECG parameters are assigned to analysis visits and study phases as described in section 3.1.2 and section 3.1.3 respectively. Evaluations with missing or partially missing dates cannot be imputed to any study phase and analysis visit.

ECG last observation on treatment is defined as last available value among those in the on-treatment analysis phase.

Change from baseline is defined as the post-baseline visit value minus the baseline value.

Additionally, ECG values will be classified as normal (if value is within normal reference range), low (if value is below the normal reference range), and high (if value is above the normal reference range) according to the below normal reference ranges:

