### **Intervention Groups and Duration:**

The screening period starts up to 42 days before the randomization visit and ends on Day -1. Eligible participants will attend 7 visits during the treatment period and 7 additional visits during the safety follow up period. Eligible participants are randomized across four different treatment arms at a 1:1:1:1 ratio for a 12-week treatment period. The planned treatment arms are: AZD8233 **CCI**, AZD8233 **CCI**, AZD8233 **CCI**, and Placebo. Participants will be dosed SC on Days 1, 8, 29, and 57.

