- a Home visits: may be undertaken at the participant’s home or any other appropriate location by site staff or by qualified external service provider. Other visits currently not designated as ‘home visits’ may also be undertaken at the participant’s home or any other appropriate location if deemed applicable, following consultation with the Investigator and the sponsor. Home visits performed by qualified external service provider (i.e. not by clinical trial site personnel) may only be performed starting Visit 5 (D22), excluding dosing visits (Visit 6 (D29) and Visit 8 (D57)).
- b Check screening labs and inclusion/exclusion criteria.
- c Weight should be measured in light indoor clothes, without shoes, after a prior visit to the bathroom.
- d Injection Site Reaction assessments to be collected based on adverse event collection criteria.
- e Vital signs and ECG to be measured pre-dose on dosing days.
- f ECG to be performed during the safety follow up period at Visits 10 (D85), 11 (D99), 13 (D127), and 15 (D155).
- g Blood samples for complement activation panel and coagulation parameters will be taken around Cmax and are to be collected pre-dose and 2 hours post-dose.
- h Samples to be obtained pre-dose on dosing days.

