## 8. STUDY ASSESSMENTS AND PROCEDURES

- Study procedures and their timing are summarised in the SoA. Protocol waivers or exemptions are not allowed. Assessments scheduled at the same time may be initiated based on the sequence below
  - 1 ECG
  - 2 Vital signs (SBP and diastolic blood pressure [DBP]), pulse rate, and temperature, if appropriate)
  - 3 PK and PD blood sampling
  - 4 Dose administrationPre-dose assessments may be performed up to 60 minutes prior to dosing.
- Immediate safety concerns should be discussed with the sponsor immediately upon occurrence or awareness to determine if the participant should continue or discontinue study intervention.
- Adherence to the study design requirements, including those specified in the SoA, is essential and required for study conduct.
- All screening evaluations must be completed and reviewed to confirm that potential participants meet all eligibility criteria. The Investigator will maintain a screening log to record details of all participants screened and to confirm eligibility or record reasons for screening failure, as applicable.
- Procedures conducted as part of the participant's routine clinical management (eg, blood count) and obtained before signing of the ICF may be utilised for screening or baseline purposes provided the procedures met the protocol-specified criteria and were performed within the time frame defined in the SoA.

The study is divided into one treatment period and one safety follow up period. The treatment period starts after the screening visits (Visit 1: Day -42 to Day -1; Visit 2: Day -7 to Day -1). During Visit 1, the participants will be checked for eligibility and enrolled to the study. Additional samples will be collected on Visit 2. Approximately 108 participants will be randomized at Visit 3 (Day 1) in a 1:1:1:1 ratio to SC injections of AZD8233 (planned doses **CCI**, **CCI**, and **CCI**) or matching placebo. AZD8233 or placebo will be administered SC on Visit 3, 4, 6, and 8. The participants will be treated for 84 days (12 weeks) with AZD8233 or placebo. Thereafter, the participants will continue in a safety follow up period for 12 weeks; the final follow up visit will be performed on Week 24 (16 weeks post last dose of AZD8233 or placebo).

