**Visit 5, 7, and 9:** For Visit 5 (Day 22  $\pm$  2 days), Visit 7 (Day 43  $\pm$  2 days), and Visit 9 (Day 71  $\pm$  2 days), are planned as clinical or home visits that may be undertaken at the participant's home or any other appropriate location by site staff or by qualified external service provider. PK sampling to be performed at Visits 7 and 9. An abbreviated physical examination is required at the visits. Vital signs, blood and urine samples to be taken at the visits.

**Safety follow up visits (Visit 10-15):** ECG must be performed at Visit 10 (Day 85  $\pm$  2 days), Visit 11 (Day 99  $\pm$  2 days), Visit 13 (Day 127  $\pm$  2 days) and Visit 15 (Day 155  $\pm$  2 days). At all safety follow up visits, an abbreviated physical examination is required, and vital signs, blood, and urine samples are to be checked. PK and ADA sampling are to be performed at Visit 10 (Day 85  $\pm$  2 days), Visit 12 (Day 113  $\pm$  2 days) and Visit 14 (Day 141  $\pm$  2 days). Visit 11, 13, and 15 are listed as home visits in the SoA. Those visits may be undertaken at the participant's

home or any other appropriate location. Other visits currently not designated as “home visits” may also be undertaken at the participant's home or any other appropriate location if deemed applicable, following consultation with the sponsor.

**Early Discontinuation Visit:** The EDV may take place any time during the study, in case a participant discontinues study treatment prior to Visit 8 (where last dose of study treatment is administered). The same assessments as during the final follow up visit will be performed. See Section 7.1.

**Final follow up visit:** The final follow up visit will be performed on Day 169 ( $\pm$  2 days). PK and ADA sampling to be performed. A complete physical examination must be performed on the visit, and body weight, BMI, vital signs, and ECG to be checked. Blood and urine sampling to be obtained.

The maximum blood volume to be drawn from each subject should not exceed 550 mL over an 8-week period. Repeat or unscheduled samples may be taken for safety reasons or for technical issues with the samples.

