**Table 5 Study phases**

Study phase	Phase Window for Analysis (Days)
Pre-treatment	before first dose of study IP (day <1 a )
On-treatment	> day 1 b to the end of study date

a Includes all measurements collected before first dose of IP. If the measurement is collected on day 1 it cannot be determined if it was done before or after the first dose of IP (due to missing time and/or planned time point), then it will be considered as collected after first dose of IP.

b Includes all measurements collected on the day of first dose of IP, at the time of IP intake and after.

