## **3.3 Efficacy, safety and exploratory variables**

The primary efficacy endpoint of the study is

1. the change from baseline in log-transformed dLDL-C compared with placebo descriptively for all visits and within a statistical model at the week 12.

The secondary efficacy endpoints of the study are:

2. the change from baseline in log transformed PCSK9 compared with placebo descriptively for all visits and within a statistical model at the week 12
3. the percent change from baseline in dLDL-C compared with placebo descriptively for all visits and within a statistical model at the week 12.
4. Correlation of LDL-C Friedewald and LDL-C Martin-Hopkins with dLDL-C
5. Level of other lipid parameters compared with placebo descriptively for all visits and within a statistical model at the week 12. Other lipid parameters include:
  - TC
  - HDL-C
  - Non-HDL-C
  - VLDL-C
  - ApoA1
  - ApoB

- Lp(a)
  - Triglycerides
  - Remnants cholesterol
6. PK parameters (to be reported in a separate report)
  7. Development of ADA and immunogenicity titre during the on-treatment and follow-up analysis phases

The safety endpoints of the study are:

8. AE
9. Vital signs

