#### **4.2.6.5 ECG**

ECG parameters are described in section 3.3.3.5. Baseline and post-baseline definitions are detailed in section 3.1.2. ECG parameters (except for the overall evaluation) will be summarized in SI units as continuous variables, at each visit and for change from baseline. Number and percentage of subjects within each QTcF intervals classes at any time during the on-treatment phase will also be reported together with number and percentage of subjects within QTcF increase classes at any time during the on-treatment phase. Overall evaluation will be analysed as shift from baseline to last value in the on-treatment phase. ECG parameters will also be listed. Overall evaluation will be listed for subjects with clinically significant abnormalities. ECG tables and listings will be based on the safety analysis set and presented for each treatment group.

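### In the complete analysis, the on-treatment ECG shift table uses the Day 169 follow-up ECG for completers, so it is mislabelled and insensitive to abnormalities that reverse after dosing

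*SAP*

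**What the plan says.** - **Phases.** SAP Table 5 has two phases, pre-treatment and on-treatment. The second starts with the first dose and runs "to the end of study date". No follow-up phase is defined.
- **Last value.** SAP 3.3.3.5: "ECG last observation on treatment is defined as last available value among those in the on-treatment analysis phase".
- **Table that uses it.** SAP 4.2.6.5: "Overall evaluation will be analysed as shift from baseline to last value in the on-treatment phase". The overall evaluation is the investigator's judgement of the ECG as normal or abnormal.
- **Dosing.** Protocol, Intervention Groups and Duration: "Participants will be dosed SC on Days 1, 8, 29, and 57".
- **ECG schedule after the last dose.** Protocol Table 1, note f, places follow-up ECGs on Days 85, 99, 127 and 155. The description of the final visit on Day 169 adds: "A complete physical examination must be performed on the visit, and body weight, BMI, vital signs, and ECG to be checked". Protocol section 8 gives the interval: "the final follow up visit will be performed on Week 24 (16 weeks post last dose of AZD8233 or placebo".
- **Other wording on phases.** SAP 3.3 item 7 reads: "Development of ADA and immunogenicity titre during the on-treatment and follow-up analysis phases". It names a phase that Table 5 does not contain.
- **Protocol on safety summaries.** Protocol 9.4.3 calls for safety variables by treatment group and visit, with frequencies for categorical data.

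**The concern.** A table described as a shift to the last on-treatment value will be read as ECG status under exposure. As defined, the complete-analysis table mostly shows ECG status at the end of a long period without dosing. Of the five scheduled ECGs after the last dose, the rule selects the one furthest from it.

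ECG is a named component of the safety objective, and this shift is the only tabulation that the SAP gives the overall evaluation. If an abnormality develops during treatment and resolves before Day 169, the table counts that participant as unchanged. SAP 4.2.6.2 handles laboratory shifts differently: it uses the maximum and minimum over the phase, so a long phase does not hide a transient change there.

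**Working it through.** **Inputs.** Last dose Day 57 (Protocol, Intervention Groups and Duration). ECGs on Days 85, 99, 127, 155 and 169 (Protocol Table 1 and the description of the final visit). Visit windows of ±2 days (Protocol Table 1). Estimated plasma terminal half-life 2 to 3 weeks (Protocol 4.2).

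**Reproducing the protocol's interval.** (169 − 57)/7 = 112/7 = 16.0 weeks, as Protocol section 8 states. With ±2 days at both visits the range is 108/7 = 15.4 to 116/7 = 16.6 weeks.

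**Distance from exposure.** Half-lives elapsed = weeks since Day 57 ÷ half-life. Fraction of the post-dose plasma level remaining = 0.5^(half-lives elapsed), assuming single-exponential decline.

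| ECG day | Weeks after last dose | Half-lives (3-week / 2-week) | Plasma level remaining (3-week / 2-week) |
|---|---|---|---|
| 85 | 4 | 1.3 / 2.0 | 40% / 25% |
| 99 | 6 | 2.0 / 3.0 | 25% / 12.5% |
| 127 | 10 | 3.3 / 5.0 | 9.9% / 3.1% |
| 155 | 14 | 4.7 / 7.0 | 3.9% / 0.8% |
| 169 | 16 | 5.3 / 8.0 | 2.5% / 0.4% |

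**Tracing one case through the planned displays.** Take a participant whose ECG is normal at baseline, abnormal but not clinically significant on Days 29 and 57, and normal on Day 169.

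- *Shift table, complete analysis:* counted as normal to normal.
- *By-visit summaries:* SAP 4.2.6.5 leaves the overall evaluation out of these.
- *QTcF classes at any time:* record the case only if QTcF itself crosses a threshold.
- *Listing of the overall evaluation:* SAP 4.2.6.5 restricts it to participants with clinically significant abnormalities, so the case is absent.
- *AE tables:* Protocol 8.2.3 does not record abnormal ECG values as AEs unless clinically significant, so the case is absent.

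If the same abnormality were clinically significant, the last two displays would be expected to show it. The gap is therefore limited to transient abnormalities that are not judged clinically significant.

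**Comparison with the protocol.** The SAP replaces by-visit frequencies of this categorical variable (Protocol 9.4.3) with a single last-value shift. The ECG entry in SAP section 6, which lists changes from the protocol, covers only the listing of individual versus averaged values and does not mention this change.

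**The case against.** The case on the other side is substantial, and much of it stands.

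- **A reader might infer that the table cannot show a treatment effect.** It can: an abnormality that persists to Day 169 appears in it. The same table is also produced at the primary analysis, triggered once everyone still in the study has completed Visit 10 (Day 85), when the last ECG may be much nearer to dosing. Participants who leave early contribute other visits.
- **A reader might infer bias toward no effect in every active arm.** The documents report no ECG effect of AZD8233, list no cardiac or QT risk in Protocol Table 2, and give no duration for such an effect. The half-life is for plasma and does not establish how long an ECG change would last. Only insensitivity to reversible abnormalities can be claimed.
- **A reader might infer that the primary and complete tables will draw on ECGs anywhere from Day 85 to Day 169.** The visits used at the primary analysis depend on cut-off rules that SAP 1.1 leaves to a charter outside these documents.
- **A reader might take SAP 3.3 item 7 as evidence that a follow-up phase was meant for ECG.** It concerns ADA only, and SAP 4.2.5.4 equates post-baseline with the on-treatment phase for ADA. It looks like leftover wording from the phase change recorded in SAP 8.1.2.
- **Other outputs cover most ECG findings, and the protocol does not ask for this shift table.** Both are true. Protocol 9.4.1 also promises raw data listings with the study report, so individual evaluations may be recoverable there. A raw listing is not a summary by arm, however, and Protocol 9.4.3 does ask for by-visit frequencies of categorical safety data.

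**Conclusion.** The point holds in a limited form. In the complete analysis, a completer's last on-treatment overall ECG evaluation is the one from Day 169, 16.0 weeks after the last dose. That is 5.3 to 8.0 plasma half-lives, with about 2.5% to 0.4% of the post-dose plasma level remaining. The label is misleading, and the table is insensitive to abnormalities that arise during treatment and reverse by the end of follow-up. Those not judged clinically significant have no other SAP-specified display of this variable.

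This rests on the participant having a Day 169 ECG (otherwise the latest available one is used) and, for the percentages only, on single-exponential decline. How many participants would be affected cannot be estimated from the documents. By-visit interval summaries, any-time QTcF counts, the listing of clinically significant abnormalities and the AE tables are untouched, so the ECG safety evaluation as a whole is not blind to treatment. This is a contained reporting defect that is worth correcting.

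**What to change.** 1. In SAP 4.2.6.5, add a shift from baseline to the worst overall ECG evaluation from first dose up to and including Week 12 (Visit 10, Day 85), or by-visit frequencies of the overall evaluation as in Protocol 9.4.3, or both. Moving the last-value cut-off to Day 85 would not be enough: an abnormality on Day 29 or 57 that had resolved by Day 85 would still be missed.
2. State explicitly that Visit 10 is included in that window. Protocol Table 1 places it under safety follow-up, while SAP 1.1 treats it as completing the treatment period.
3. Keep the last-value shift, but label it end of follow-up in the complete analysis.
4. Reconcile SAP Table 5 with SAP 3.3 item 7, either by defining a follow-up phase or by removing the reference to one.
5. If by-visit frequencies are not adopted, record that departure from Protocol 9.4.3 in SAP section 6.

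The cost is a few lines of SAP text and one extra table or column. The ECG evaluations are already scheduled and collected, so no new data are needed.

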**Table 7 ECG normal reference ranges**

Parameter	Normal Reference Ranges
RR	600 -1200 msec
PR	120 – 200 msec
QRS	80 – 120 msec
QT	350 – 430 msec
QTcF	320 – 470 msec
Heart rate	50 – 100 beats/min

QTcF intervals are classified also as:

- $\geq 450$  msec
- $\geq 480$  msec
- $\geq 500$  msec

QTcF increases respect to baseline are classified as:

- $\geq 30$  msec
- $\geq 60$  msec
- $\geq 90$  msec

### 3.3.4 Exploratory endpoints

#### 3.3.4.1 Lipoprotein profile

Lipoprotein profile parameters are:

- VLDL Subclass  $>200$  nm-Trigl.
- VLDL, Large-Trigl.
- VLDL, Medium-Trigl.
- VLDL, Small-Trigl.
- Low Density Lipoprotein Particle Conc.

- Intermed.Dens. Lipoprot. 25+/-2 nm-Chol\*
- Low Density Lipoprotein, Large-Chol.
- Low Density Lipoprotein, Small-Chol.
- HDL Particles
- High Density Lipoprotein, Large-Chol\*
- Medium HDL
- High Density Lipoprotein, Small-Chol\*
- Very Low Density Lipoprotein, Mean
- Low Density Lipoprotein, Mean
- High Density Lipoprotein, Mean
- Triglycerides
- VLDL-Triglycerides
- HDL-Cholesterol Direct\*
- Lipoprotein Insulin Resistance Score
- Apolipoprotein A-I
- Apolipoprotein B
- Non-HDL-Cholesterol

Lipoprotein parameters are assessed in a central laboratory and assigned to the analysis visits and analysis phases as described in section 3.1.2 and 3.1.3. Measurements with missing or partial missing dates are not assigned to any analysis visit / analysis phase.

Change from baseline is calculated as the visit value minus the baseline value.

### **3.4 Exposure and treatment compliance**

As per study protocol, subjects start the subcutaneous injections of the study IP at day 1. Then the subjects will be subcutaneously dosed also on Days 8, 29, and 57. Subcutaneous injections should primarily be performed on site. Dosing visits may be undertaken as home visits. If participants are dosed at home, they will receive the study intervention directly from the nurse.

The date, and time if applicable, of dose administered in the clinic and at home, as well as the anatomical location of the injection site, will be recorded in the eCRF.

